- 12) Pregnancy or Breast feeding. All female in reproductive age will undergo pregnancy tests. Female participants will be required to provide evidence of use of contraceptives during the course of the study.
- 13) Unable to understand the design and requirements of the study
- 14) Unable to sign the informed consent for any reason
- 15) An assigned responsible adult has provided assent to assist in patient's study participation. The responsible adult agrees to be present at each study appointment as well as provide transportation to study appointments for the patient.

Non responders

If a patient does not respond to the study treatment by their 4th treatment they will be removed from the study due to non-response. A successful response to study treatment will be at least a 30% reduction in MADRS scores from screening until the 4th treatment. Again if a patient does not respond by the 4th treatment, they will be excluded from the study.

Unanticipated Hospitalizations

If a patient needs to be hospitalized for worsening of symptoms or for their own personal safety, they will be removed from their study participation and their study treatment will end at that time.

Feasibility

Subject recruitment: Our center has access to a large patient pool (drawing from a metropolitan area of about 5.5 million people) and well-established ability to recruit patients with mood disorders. [name] is the department chair for Psychiatry and Behavioral Sciences and Director of the University of Texas, Center of Excellence on Mood Disorders. He successfully completed a large number of studies over the past 20 years with excellent recruitment of MDD and BD subjects at this site. We will also recruit participants through doctor referrals. Participants will be exclusively outpatients.

Funding of the study: given the preliminary nature of this study we plan to use departmental funding for the current study and then possibly apply for a larger grant later on once we have collected preliminary data and calculated optimal power/effect sizes for ketamine treatment in individuals with TRD.

Data analysis

Normality assumptions for continuous variables will be examined. Where appropriate, outliers will be winsorised and log, square root or reciprocal transformations applied to achieve normality if appropriate. If normality cannot not been achieved, either untransformed or dichotomized scores were used. Baseline characteristics will be compared between responders and non-responders with the Mann-Whitney U test for continuous variables and the chi-square test for categorical variables. Changes between two time-points for continuous variables were tested with paired t tests, and associations between continuous variables will be quantified with the Spearman correlation coefficient. Random effects models will be performed to quantify changes in clinical score and its component items over time and to compare temporal differences between eventual responders and non-responders. Splines will be used to determine differences in the pattern of response over time among all patients and to identify the time at which there was no additional improvement in depressive symptoms. Additionally, the relationship between response status between baseline and end of study calculating sensitivity, specificity, and positive and negative predictive values will be reported. Time to relapse for patients who met response criteria at end point will be estimated with the Kaplan-Meier method. Analyses will be performed with IBM SPSS Statistics (version 19; SPSS, Chicago, Illinois) and SAS (version 9.2; SAS, Cary, North Carolina).

Study timetable

Activities	Months											
	1	2	3	4	5	6	7	8	9	10	11	12
Obtain IRB approval at UTHealth and HCPC		x	x									
Set up the Ketamine Ambulatory Clinic at HCPC			x	x								
Start recruiting patients and collecting data					x	x	x	x				
Analyses of initial dataset								x	x	x		
Submit a poster to International meeting with final results									x	x	x	
Submit result to high-impact peer-reviewed journals											x	x

Importance of the knowledge to be gained

Our findings will enhance our understanding of the safety, tolerability and efficacy of ketamine infusion in adults with TRD. Further it will help us understand the feasibility of this treatment in a psychiatric setting. The findings of the present study will also constitute an important foundation for future grant proposals investigating the efficacy of this intervention as a measure of suicide prevention.

*Women and Minority Inclusion in Clinical Research**Inclusion of Women*

The subjects will include males and females, ages 18-65 years old, from various race/ethnic backgrounds, as reflected in the local community in the greater Houston area.

Inclusion of Minorities

Our study will include minority groups in proportions that will be representative of the ethnic/racial composition of the local community in Houston, Texas. Our projected numbers for minority enrollment are detailed in the enrollment table attached.

Inclusion of Children

Children will not be included in the study. The inclusion of children at this early stage would increase substantially the number of subjects needed for the overall project. At this time, we will focus on an adult population (ages 18-65 years old), which will also allow us to limit some of the potential confounding factors to our brain imaging and neurocognitive findings. Depending on our results these investigations will be extended to children and individuals over 65 years old in future studies.

Prisoners and pregnant women

We are aware of the special protections afforded to prisoners per federal regulations. We will not actively recruit people who are incarcerated to participate in this study. We do, however, acknowledge the possibility of research participants in our target population being incarcerated during the study. If an active participant is incarcerated for an extended period of time, disenrollment from the study will be necessary. No research interaction or intervention will take place until an incarcerated participant is released from jail. Finally, neither pregnant woman nor neonates will be enrolled in this study.

Potential Risks

Loss of confidentiality is a highly unlikely but potential risk associated with this study. Some participants may find questions annoying or intrusive and neuropsychological testing might induce some fatigue and sensation of boredom. The venipuncture (insertion of small IV due to need for IV infusion of ketamine) might produce some mild pain, bruising, bleeding, infection, and in some cases even induce fainting. Side effects associated with ketamine injection are rare and, if any, of transient duration. The most commonly reported side effects during the 4-hour period after each infusion include feeling strange or unreal (58.3%), abnormal sensations

(54.2%), blurred vision (50.0%), feeling drowsy or sleepy (45.8%) (Murrough et al., 2013b) and headaches (30-40%) (aan her Rot et al., 2010). Based on previous evidence we do not expect ketamine to impair cognitive functions such as memory, attention and language (aan her Rot et al., 2010).

One third of the patients exposed to standard repeated infusions of IV ketamine reported some kind of hemodynamic change such as elevated blood pressure (BP) and/or heart rate (Murrough et al., 2013b) that usually resolves shortly after the ketamine infusion (aan het Rot et al., 2010; Murrough et al., 2013b). It has been reported that initial hypertensive episodes and transient tachycardia are predictive of hemodynamic changes with subsequent repeated ketamine infusions (aan het Rot et al., 2010). Ventricular premature contractions, hypotension, and non-significant changes in oxygen saturation have also been reported with low-dose (0.5mg/kg) ketamine infusions over 40 minutes.

Risk of other medications

If patients are currently taking certain medications on a daily basis within 24 hours prior to and / or after receiving ketamine, they will not be able to take these medication(s) while receiving a ketamine infusion without clearance or approval of the physicians involved in administering ketamine. This is due to concerns for potential increased sedation and / or trouble breathing.

Medications include:

- Sedatives (e.g., clonazepam, lorazepam, alprazolam)
- Antibiotics (e.g., azithromycin, clarithromycin)
- Antifungal agents (e.g., ketoconazole)
- Tramadol

Potential Benefits

There are direct potential benefits for the individual subject as a result of participating in the planned work. First of all, ketamine serial IV infusions will alleviate potentially disturbing, life-threatening depressive symptoms such as suicidal ideation. Moreover, participants might be able not only respond but also remit from other resistant/refractory depressive symptoms that reduce their quality of life and everyday functional outcome. There are no direct benefits associated with the completion of questionnaires, simple computer tests, and routine medical diagnostic and treatment procedures. Therefore we believe the risk-benefit ratio to be favorable for every subject involved in this naturalistic study.

Potential subjects will contact the UTHealth Center of Excellence on Mood Disorders group in response to flyers, advertisements or recommendation from their attending psychiatrist treating TRD or TRBD. Potential participants will undergo a brief telephone screening. If they meet the eligibility criteria and are still interested in taking part in the study, a first appointment will be scheduled to discuss the study with the researchers. If suitable the participant will be asked to read and signs the consent document if all questions have been discussed and answered to the potential subject's satisfaction.

Data and Safety Monitoring Plan

This study will be performed in accordance as provided by law under the resolution N° 008430 of 1993 emitted by the Ministry of Health about medical research focused on health issues. This is a low-risk project in terms of ethical concerns.

This study will acquire, use and create individually identifiable health information (known as Protected Health Information or PHI). Confidentiality will be protected at all times by having research records identified by code number only. All research information will be stored in locked files at all times. Only authorized research staff will have access to the information gathered in this study. Only subjects capable to provide consent will be included in the study.

As per the Health Insurance Portability and Accountability Act (HIPAA) all individuals who are eligible and agree to participate in this research study will be required to sign a HIPAA research authorization prior to participation. If an individual refuses to sign the HIPAA research authorization, they will not be able to participate in this study. The HIPAA form is part of the official consent form.

Data will be stored separately from participants' identifiers. Both will be stored on encrypted drives on computers in locked offices. Confidentiality will be protected by having research records identified by code number only. All research information will be stored in locked files at all times. Only authorized research staff will have access to the information gathered in this study. All paper data will be stored [REDACTED]

[REDACTED] in a double locked cabinet. The electronic data will be stored [REDACTED]
[REDACTED]
[REDACTED].

An Accounting of Disclosure (AOD) will be created and maintained for any disclosure of individually identifiable information (III) outside the UTHSC-Houston. The manual spreadsheet will include the date of the disclosure, nature or description of the III disclosed purpose of each disclosure and the name and address of person or agency to which the disclosure was made.

The study imparts only minimal risk to included subjects. Strict monitoring of hemodynamic and respiratory changes as well as psychiatric screening will be performed during each infusion of ketamine.

Reimbursement

Patients will pay for the ketamine treatment (\$400 for each of the 12 injections that are part of the main treatment, \$400 for each maintenance treatment) and no reimbursement will be provided for their participation in the study.

Currently costs related to this study are not likely to be covered by insurance, and a proportion of eligible candidates may not be able to participate. It is however important to highlight that determining the effectiveness of a promising treatment for a severely ill patient group such as TRD-- for whom standard treatments have failed – has significant clinical relevance and needs to be tested in a timely fashion.

References

aan het Rot M, Collins KA, Murrough JW, Perez AM, Reich DL, Charney DS, Mathew SJ. Safety and efficacy of repeated-dose intravenous ketamine for treatment-resistant depression. *Biol Psychiatry*. 2010 Jan 15;67(2):139-45.

Beck AT, Kovacs M and Weissman A. Assessment of suicidal ideation: The Scale for Suicide Ideation. *J Consult Clin Psychol* 1979;47: 343–352.

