7. Experience no cognitive impairment on the Brief Assessment of Cognition in Affective Disorders (BAC-A) following ketamine infusions. To our knowledge this hypothesis has not been previously assessed after an 8-week serial ketamine infusion treatment period.

Clinical relevance

Treatment Resistant Depression (TRD) is a major public health problem that constitutes a great burden for patients and mental health providers because of its prevalence, impact on people's quality of life and overall cost to the society (Nemeroff et al., 2007). Given the dearth of the research in the field of Ketamine treatment, more naturalistic follow-up studies focusing on ketamine's innovative antidepressant properties are warranted. Further, the findings of this study will provide health professionals with additional knowledge on the antidepressant properties of repeated ketamine IV infusions in both resistant Major Depressive Disorder (MDD) and Bipolar Disorder (BD). The current study will also help characterize responders from non- responders to ketamine, and will enable the assessment of the response and remission rates following ketamine intervention.

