Ketamine infusions do not appear to have negative neurocognitive sequels. In a recent study, 15 patients with TRD underwent six IV infusions of 0.5 mg/Kg ketamine over 40 min, (three times a week during a 12-day period) followed by a 4-wk observational period. Following the last ketamine infusion the authors observed an improvement in visual memory and working memory. These cognitive changes may have been due to the decrease in the severity of the depressive symptoms (Shiroma et al. 2014). Along the same line, Murrough et al. (2015) found no change in cognitive functioning 7 days post-ketamine treatment in individuals with treatment-resistant depression.

To the best of our knowledge, the only published study exploring the tolerability, safety, and efficacy of repeated-dose open-label IV ketamine (six infusions over 12 days) focused on 10 medication-free symptomatic patients with TRD who had previously shown a meaningful antidepressant response to a single ketamine dose (Aan het Rot, et al., 2010). Patients received a 40-min IV infusion of ketamine (0.5 mg/kg) in an inpatient setting with continuous vital-sign monitoring and repeated recording of adverse events such as psychotomimetic effects. In the event that patients showed a 50% reduction in MADRS scores on day 2, they received five additional infusions on an outpatient basis on days 3, 5, 8, 10, and 12. Follow-up visits were conducted twice weekly for 4 weeks or until relapse. Ketamine elicited minimal transient positive psychotic or dissociative symptoms. Side effects during and after each ketamine infusion although common were reportedly mild. The response criterion was met by nine patients after the first infusion as well as after the sixth infusion of ketamine. MADRS scores after the sixth ketamine infusion were reduced by 85%, and an 89% relapse rate was reported between weeks 3 and 4 after finishing repeated IV ketamine infusion.

To summarize, these findings confirm the feasibility of low concentration and slower infusion rate of repeated-dose IV ketamine infusions for the acute treatment of TRD in the clinical practice (Aan het Rot, et al., 2010; Murrough et al., 2013b; Rasmussen et al., 2013).

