Thus, in the current study we want to naturalistically explore the antidepressant effects of serial slow IV infusions (40 minutes) of ketamine at a dose of 0.5 mg/kg, over a treatment period of 8 weeks in an academic psychiatric hospital. This is a minimal sedation treatment. This dosage is the highest used so far in the literature and was selected because of its reported benefits in a psychiatric population. The dosage will be calculated using the patient's weight in kilograms. For dosing purposes, 0.5-0.9 round up to the next dose and from .01-0.49, we will round down to the lower dose. The primary outcome measure of this study will be *remission* estimated based on the severity of depressive scores (MADRS). After the 8 weeks of treatment, there will be a four week observational period. During the observational period, participants will receive treatment as usual and will be contacted over the phone for follow-up questions regarding their overall health status, mood and clinical state using MADRS, YMRS and CGI. They will also complete a neurocognitive task at the end of the 4 week observational period.

B. Innovation

The approach taken in the current study is novel for two reasons: 1) we are testing a novel dosage and time of infusion for the administration of slow infusion, repeated IV ketamine targeting TRD; 2) this is the first naturalistic study of repeated ketamine IV infusion for MDD and BD in a psychiatric setting. Furthermore, this will constitute the largest study conducted to date testing the antidepressant effects of repeated ketamine infusions in a combined population of MDD and BD patients with TRD.

C. Approach

The current project will exploit the feasibility of recruitment associated with ongoing studies at the University of Texas, Center of Excellence on Mood Disorder, Department of Psychiatry and Behavioral Science in Houston aimed at identifying the neural correlates of BD. The clinical sample will include individuals from various ethnic/racial backgrounds, reflecting the local community in the greater Houston area. We will use slow infusions of ketamine over a time

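### Remission is the declared primary outcome but has no cut-off, visit, denominator or planned analysis, and end-point response is also undefined where the analyses use it

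*Combined protocol and SAP*

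**What the plan says.** All places are in the combined protocol and SAP.

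- **Primary outcome** (2.0 Research Strategy, end of A. Significance): this is named as remission, "estimated based on the severity of depressive scores (MADRS"). No cut-off score, visit or analysis population follows.
- **Aim** (Clinical relevance): the study "will enable the assessment of the response and remission rates following ketamine intervention". No method is attached.
- **Removal** (under the Non responders heading, which opens with the rule itself): "If a patient does not respond to the study treatment by their 4th treatment they will be removed from the study due to non-response". The threshold is then given: "A successful response to study treatment will be at least a 30% reduction in MADRS scores from screening until the 4th treatment". Under Unanticipated Hospitalizations, patients admitted for worsening or for their own safety also leave.
- **Data analysis**: the section lists tests by responder status, paired t tests, Spearman correlations, random effects models, splines, predictive values and Kaplan-Meier. Remission is in none of them. Response is used repeatedly, for example "Baseline characteristics will be compared between responders and non-responders with the Mann-Whitney U test for continuous variables" and "Time to relapse for patients who met response criteria at end point", without a criterion.
- **Literature** (A. Significance): for one 10-patient series on the conventional 12-day scheme, "In the event that patients showed a 50% reduction in MADRS scores on day 2", five more infusions followed. Nine of the ten then met that series' response criterion.
- **Hypothesis 1** expects efficacy similar to conventional schemes as a class.

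**The concern.** A primary outcome without a definition or an analysis gives no pre-set primary result. The study is open label, and MADRS is rated at weeks 4, 8 and 12 and at weekly calls after treatment ends, so the cut-off and the visit could be settled after scores are known.

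The removal rule makes the denominator matter as well. It takes out patients with little early improvement, who are the least likely to remit. A rate computed on those still in the study at week 8 describes a group already selected for response.

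The same gap affects response. The Data analysis section relies on eventual responders, on response status at the end of the study and on response at end point, and defines none of them. The 30% figure is the only candidate, and it was written for another time and purpose.

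At stake is the purpose given under Study design: an effect size for a later randomised trial. An effect size on an outcome that is not fixed cannot plan that trial.

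**Working it through.** The plan has no figure to reproduce: Study design states that no power or effect size was calculated for the 30 patients. Four checks were made instead.

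**1. Outcome against analyses.** Each method in Data analysis was matched with the outcome it serves. They cover change in scores over time, responder status and time to relapse. None gives a remission proportion.

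**2. Denominator.** Inputs: 30 planned patients (from the objectives); 9 remitters and the number retained (both assumed). Removed patients are taken not to remit. The rate is x/n, and the exact 95% CI runs from Beta⁻¹(0.025; x, n−x+1) to Beta⁻¹(0.975; x+1, n−x).

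| Removed (assumed) | Rate | Exact 95% CI |
|---|---|---|
| Counted as non-remitters | 9/30 = 30% | 15% to 49% |
| 3, dropped | 9/27 = 33% | 17% to 54% |
| 6, dropped | 9/24 = 38% | 19% to 59% |
| 10, dropped | 9/20 = 45% | 23% to 68% |

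The rate is multiplied by 30 divided by the number retained; with 10 removed, 30/20 = 1.5.

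**3. Cut-off and visit.** Assumed: whole-number week-8 MADRS scores from a normal with mean 15 and SD 9. P(score ≤ c) = Φ((c + 0.5 − 15)/9).

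- c = 7: Φ(−0.83) = 20%
- c = 10: Φ(−0.50) = 31%
- c = 12: Φ(−0.28) = 39%

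If remission at any visit counted, six ratings would be available: week 4, week 8 and weeks 9 to 12, taking the last call as the week-12 rating. They were simulated with correlation 0.7, SD 9, means rising from 15 at week 8 to 19 at week 12, and a week-4 mean varied from 15 to 22. The any-visit rates are 34% to 38%, 48% to 52% and 57% to 61% for the three cut-offs. All of these distributions are assumed, and removal is ignored.

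**4. Response threshold.** Assumed: percentage MADRS reduction is normal with mean 45 and SD 30.

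- At 30%: 1 − Φ((30 − 45)/30) = 69%
- At 50%: 1 − Φ((50 − 45)/30) = 43%

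The gap is 26 points. With means of 30 to 60 and SDs of 20 to 35 it runs from 19 to 38 points. The two thresholds are not interchangeable. The published 9/10 itself has an exact 95% CI of 55.5% to 99.7%.

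**A timing point.** At two infusions a week, the 4th falls at about 4/2 = 2 weeks. The first post-baseline MADRS in the schedule is at week 4, so the removal rule has no scheduled rating behind it.

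**The case against.** The strongest reply is that this is a preliminary, single-arm study with no planned test, that it states an aim to assess remission rates, and that the primary outcome is named between two mentions of the 8-week treatment period, so week 8 is the natural reading. Week 8 is indeed the likely intention. It is not stated, however, and a likely visit supplies neither a cut-off nor a denominator.

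A reader might infer more than the documents support:

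- *Every responder analysis uses the 30% threshold.* Data analysis never cites it. At least two analyses use response at end of study or at end point, which is not the 4th treatment. What can be shown is that the criterion is missing.
- *The comparator uses 50%.* Hypothesis 1 names a class of schemes. The 50% figure is given for one 10-patient series, as a day-2 gate to further infusions; its role as that series' response criterion is only implied. The larger 24-patient series has no threshold in the text.
- *The plan will report a lenient rate beside a stricter one and call them similar.* No formal comparison with a published series is planned.
- *Removed patients are dropped from the analysis.* They leave the study, but comparisons with non-responders imply that some of their data are kept. The denominator is open rather than fixed at the retained patients.

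It is also fair to say that every magnitude above rests on assumed distributions or counts.

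**Conclusion.** The point holds in this form: remission is primary but undefined and unanalysed, and end-point response is undefined where it is used. The 30% removal figure is the only in-study candidate for response, and it differs from the 50% quoted for one cited series. Nothing in the documents shows that 30% will be used at end point, or that 50% is the general comparator.

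On size, the denominator alone could move the same 9 remitters from 30% to 45%, if 10 patients are removed and none of them would have remitted. Cut-off alone could move remission from 20% to 39%, and free choice of visit as well could take it to about 60%, under the assumed scores. These figures illustrate the latitude that the plan leaves; they do not predict its results. The absence of a definition and of an analysis rests on the text alone and needs no assumption.

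**What to change.** 1. **Primary analysis.** Estimate the proportion with MADRS at or below one cut-off, fixed before data are seen, at week 8, among all patients who received at least one infusion. Count patients removed early, for non-response or hospitalisation, and those without a week-8 score, as non-remitters. Report an exact 95% CI; with 30 patients and 9 remitters it would run from 15% to 49%.
2. **Response.** State one end-point criterion for the responder, relapse and literature analyses, separate from the removal rule. At least a 50% reduction from baseline at week 8 would match the one threshold quoted for a conventional series.
3. **Literature comparison.** Call it descriptive. Even at 50%, the 9/10 was observed after six infusions over 12 days in patients who had already responded to a single dose, whereas week 8 here follows up to 2 × 4 + 1 × 4 = 12 infusions.
4. **Removal rule.** This point asks for no change to it and takes no view on its threshold. The rule and the MADRS schedule must be reconciled, because no rating is scheduled at the 4th treatment.

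Items 1 to 3 change analysis wording only and need no new data. The cost is a less favourable headline remission or response rate.
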